1. STUDY PROTOCOL

Title:	A double-blind, partial cross-over, incomplete factorial study to assess the local anesthetic efficacy and safety of CTY-5339 Anesthetic Spray (CTY-5339-A) when applied to the cheek mucosal tissue in normal volunteers
Test Drugs:	CTY-5339-A (14.0% benzocaine, USP, 2.0% tetracaine HCL, USP) CTY-5339-CB (14.0% benzocaine, USP) CTY-5339-P (Vehicle Spray) (1 metered spray will deliver \approx 200 μ L containing either benzocaine 28 mg + tetracaine HCl 4 mg or benzocaine alone 28 mg or vehicle.)
Methods:	Single-center, randomized, double-blind, partial cross-over, incomplete factorial design. Pin Prick and QST Heat (QST) will be utilized to assess efficacy. Assessment of ECGs, pulse oximetry, and methemoglobinemia (blood co-oximetry) will be utilized to assess safety. ECGs and blood sampling will be performed at Baseline and after 1 hour of treatment. Pulse oximetry will be performed at Baseline and every 10 minutes through 1 hour after treatment.
Sponsor Name and Address:	Cetylite Industries, Inc. [name]
Protocol Identification:	C-002
Development Phase IIb:	Proof-of-Concept Experimental Pain Model
Company/Sponsor Representative:	[name] [name] [contact]
Compliance Statement:	The study will be conducted in accordance with the ethical principles that have their origin in the Declaration of Helsinki and with standards of current Good Clinical Practice, as defined by

	the International Conference on Harmonization and all applicable FDA regulations.
--	---

Date	Version	Comment(s)	Author
April 20, 2016	2.0	Draft	[name]
April 27, 2016	3.0	Draft- ([name], [name], [name])	[name]
May 2, 2016	3.1	Draft- ([name], [name], [name])	[name]
May 7, 2016	4.0	Draft- ([name], [name], [name], [name], [name])	[name]
May 7, 2016	4.1	Draft- ([name], [name], [name], [name], [name])	[name]
May 7, 2016	4.2	Draft- ([name], [name], [name], [name], [name])	[name]
May 10, 2016	4.3	Draft- ([name], [name], [name], [name], [name])	[name]
May 16, 2016	4.4	Draft- ([name], [name], [name], [name], [name])	[name]
May 18, 2016	4.5	Draft- ([name], [name], [name], [name], [name])	[name]
May 25, 2016	4.6	Draft- [name] Edits	[name]
June 9, 2016	4.7	Minor Edits Prior to sign-off Final Version	[name]/[name]
August 8, 2016	5.0	Incorporation of Amendment 1 Changes/Edits	[name]
October 17, 2016	6.0	Incorporation of Pulse Oximetry and Stopping Rules	[name]/[name]

3. CLINICAL PROTOCOL SYNOPSIS

TITLE: A double-blind, partial cross-over, incomplete factorial study to assess the local anesthetic efficacy and safety of CTY-5339 Anesthetic Spray (CTY-5339-A) when applied to the cheek mucosal tissue in normal volunteers

STUDY NUMBER: C-002

PRINCIPAL INVESTIGATOR: [name], Director Clinical Pharmacology Research Unit, Dept. of Oral and Maxillofacial Surgery/Pharmacology, University of Pennsylvania, School of Dental Medicine

SITE: University of Pennsylvania, School of Dental Medicine
[name].

STUDY OBJECTIVES: This study is designed to assess the efficacy and safety of locally applied CTY-5339 Anesthetic Spray compared to 14.0% benzocaine alone in normal volunteers using experimental sensation including pinprick with a needle (PPT) and heat sensation threshold (QST). The objective of this study is to demonstrate that the combination of the two constituents in the CTY-5339 Anesthetic Spray (CTY-5339-A) provides longer acting local anesthesia than 14.0% benzocaine alone (CTY-5339-CB). The primary objective is to demonstrate that the CTY-5339-A one-spray dose is superior to CTY-5339-CB. The secondary objective is to demonstrate that the CTY-5339-A up to two sprays is a safe dosage.

HYPOTHESIS: CTY-5339-A when locally applied to cheek mucosal tissue in the mouth will have an onset comparable to the fastest constituent, benzocaine, and a prolonged effect comparable to the longest acting constituent, tetracaine, of the combination product. The study also is designed to demonstrate that both the CTY-5339-A one- and two-spray dosages are safe. (The assumption being made is that benzocaine has a faster onset of action than tetracaine.)

**STUDY
DESIGN:**

This is a single-dose, partial cross-over, double-blind and single-center study with an active control treatment. All subjects will remain at the study center for each of the two 60 minute test sessions. The subjects will be tested at two different test sessions separated by 4-14 days.

The study will include 76 subjects who will be evaluated for 60 minutes at each test session. At each session, a circular area of approximately one inch in diameter will be isolated on one side of the inner cheek using an indelible oral pencil. Each session will use a different side of the cheek. The possible sequences of treatments with the metered spray at the two sessions are:

Session 1		Session 2	
Formulation	Sprays	Formulations	Sprays
CTY-5339-A	1	CTY-5339-CB	1
CTY-5339-A	2	CTY-5339-CB	1
CTY-5339-CB	1	CTY-5339-A	1
CTY-5339-CB	1	CTY-5339-A	2

To maintain double-blind conditions, the CTY-5339-CB subjects in the two spray sequences will also receive one spray with the vehicle control (CTY-5339-P). A third party not involved with evaluating subjects will administer the drug. The CTY-5339-P Vehicle will be sprayed outside the circumscribed area to avoid dilution of active drug. Efficacy evaluations will be done at 1-5 minute intervals beginning immediately after drug administration and will include:

Pin Prick (PPT) & QST Heat Sensation Tests:

For PPT, evaluations will be done at 1 minute intervals for the first 5 minutes to capture onset of anesthesia. Starting at 5 minutes after drug administration, both PPT and QST will be done at 5 minute intervals up to the one hour time point. If there is no indication of anesthesia by 10 minutes, the subject will be considered a treatment failure and the assessment of PPT and/or QST, as appropriate, will be discontinued. In addition, once onset of anesthesia has occurred, if there is no longer any anesthesia at two consecutive evaluation time points from 10 minutes onward, the assessment of PPT and/or QST, as appropriate, will be discontinued.

STUDY

Pin Prick Test (PPT): The PPT will be assessed, using a 90-mm, 26-

DESIGN: (cont) 1 gauge pencil-point spinal needle (Polymedic; Temena S.A., Bondy, France or equivalent). At screening, 3 pin pricks will be performed on each cheek. Pin pricks will be assessed using a 0 (no pain) to 10 (severe pain) Numerical Rating Scale (NRS). In order to be eligible for the study, for each cheek, subjects must have a minimum score of "3" for the last 2 pin pricks, and one of those scores has to be "4" or higher.

During each treatment session, at Baseline and at each post-dosing time point, 3 pin pricks will be performed first on the non-treated cheek and then on the treated cheek. At Baseline, pin pricks on both cheeks will be assessed using a 0 (no pain) to 10 (severe pain) NRS. Post-Baseline, pin pricks on the non-treated cheek will also be assessed using the 0 to 10 NRS, but on the treated cheek, the three repetitions will be compared to the non-treated cheek as "No pain", "Less Pain" or "Similar/More Pain". For each cheek, the first pin prick will not be used for analysis. Of the remaining 2 pin pricks, the one with the most severe pain rating will be used for analysis. During each treatment session, in order for a subject to be eligible to continue in the study, for each cheek, both of the last 2 Baseline assessment pin pricks must have a minimum score of "3" for the last 2 pin pricks, and one of those scores has to be "4" or higher. Post-Baseline, an assessment of "No Pain" or "Less Pain" at a drug application site will be recorded as presence of analgesia/anesthesia ("Responder").

Heat sensation threshold (QST-Heat): The heat stimuli are delivered in 3 repetitions, with inter-stimulus intervals of 30s. The basal thermode temperature is set at a comfortable 35°C. The rate at which the thermode heats up is set at 0.5°C/s, while the rate at which it cools down is set at 8°C/s. The maximum thermode temperature is set at 51°C. (Note: Hot beverages such as tea and coffee are frequently served at temperatures between 50°C - 60°C. Burns can occur at 65°C.²⁵). Heat sensation threshold will be defined as the temperature at which the subjects first feel tingling, warmth, heat, or pain.

At screening, QST-Heat assessments will be performed on each cheek. In order to be eligible for the study, for each cheek, subjects must have a mean Heat sensation threshold of 48.5°C or less, based on the last 2 of the 3 readings.

During each treatment session, for each assessment, the first stimulus will be disregarded and the remaining two stimuli will be averaged for data analysis (unless the first two readings are 51°C, in which case the third assessment will not be done). At Baseline and at each post treatment assessment, the heat sensation threshold will be performed on the treated cheek only. During each treatment session, in order for a subject to be eligible to continue in the study, subjects must have a

**STUDY
DESIGN: (cont)**

mean Heat sensation threshold of 48.5°C or less, based on the last 2 of the 3 readings. Post-Baseline, the presence of analgesia/anesthesia will be defined when the heat sensation threshold at the treated site is higher than the Baseline (“Responder”).

All tests on the treated cheek will be done near the center of the circumscribed area, but in a slightly different place at each consecutive evaluation time point. All tests on the non-treated cheek will be performed at approximately the same part of the cheek as those on treated cheek.

Randomization: A randomization code will determine the sequence of treatments and to which circumscribed area the treatment is administered (left or right cheek). Sensory testing will be done in the following order: pin prick followed, where applicable, immediately by heat sensation tolerance.

Subjects retain the right to withdraw from the study at any time.

EFFICACY MEASUREMENTS

The primary comparison of interest is one spray of CTY-5339-A compared to one spray of CTY-5339-CB. Co-primary efficacy variables are duration of effect as determined by PPT and duration of effect as measured by QST Heat. Duration of effect is defined as the time (in minutes) from onset to treatment failure (for PPT, treatment failure occurs when an assessment of “Same/More” pain, and for QST, a treatment failure occurs when the average heat temperature is the same or less than the average heat temperature at Baseline up to the 60-minute time point (at two consecutive time points).

The secondary efficacy variables include:

- Duration of anesthesia (PPT and QST Heat) for the two sprays of CTY-5339-A compared to one spray of CTY-5339-CB plus CTY-5339-P
- Duration of anesthesia (PPT and QST Heat) for the two sprays of CTY-5339-A compared to one spray of CTY-5339-A
- Onset of anesthesia for PPT and QST Heat
- Percentage of responders for PPT and QST Heat for both onset and duration
- Percentage of responders for PPT and QST Heat at each time point

OTHER MEASUREMENTS

At Baseline and at the end of the 60-minute test session an ECG, vital signs, and a 7 mL blood draw will be taken. The blood will be analyzed for the occurrence of subclinical methemoglobinemia by the HUP – Pepper Lab via co-oximetry analysis. At screening and throughout each test session, subjects will also be monitored with pulse oximetry. Methemoglobinemia is being defined as >5% of a subject’s

hemoglobin in the methemoglobin state, or a pulse oximetry reading of less than 91%.

ESTIMATED DURATION OF SUBJECT PARTICIPATION IN THE STUDY:

The subjects will be tested on two separate occasions. Each session will take approximately two hours total time; however, the actual efficacy testing will take 60 minutes. There will be 4-14 days spacing between visits. A phone follow-up will occur 3 days (\pm 1 day) and 15 days (\pm 2 days) after the subject completes Sessions 1 and 2, respectively. If there are any adverse side effects, at the discretion of the PI, the subject may be asked to return to the study site for evaluation.

DURATION OF STUDY:

The study will be completed when the last subject completes the last follow up phone call. The expectation is that the study will be completed within 4-6 months of the first subject entry.

NUMBER OF SUBJECTS:

Up to 150 male and female subjects will be screened in order to enroll up to 76 ASA Category I or II subjects. The total number of exposures to study medication will be 152 (76 subjects x 2 exposures). Each of the CTY-5339-A treatment regimens will have 38 exposures and the CTY-5339-CB will have 76 exposures.

SAMPLE SIZE DETERMINATION:

The sample size was selected based on evaluating a reasonable number of subjects to determine whether CTY-5339-A has a longer duration of action than CTY-5339-CB, which contains 14.0% benzocaine only.

DOSAGE:

(specific gravity is slightly less than 1; therefore 200 μ L is an approximate volume.)

CTY-5339-A 1-metered spay = 200 mg total (\approx 200 μ L)
Benzocaine 28 mg + Tetracaine HCl 4 mg

CTY-5339-A 2-metered spays = 400 mg total (\approx 400 μ L)
Benzocaine 56 mg + Tetracaine HCl 8 mg

CTY-5339-CB = 200 mg (\approx 200 μ L)
Benzocaine 28 mg

INCLUSION CRITERIA:

- a. Male and female subjects between 18-75 years of age with a Body Mass Index (BMI) \leq 32;
- b. Subjects are ASA Category I or II and are in good physical health as judged by physical and laboratory examinations;
- c. Subjects with normal appearance of the oral mucosal tissues;
- d. At screening and at Baseline during Session 1, subjects with PPT scores on both cheeks of at least "3" (on a 10 point NRS) on the last 2 of 3 readings, 1 of which must be a score of at least "4";
- e. Subjects with mean QST Heat sensation temperature assessments

on both cheeks of 48.5°C or less based on the average of the last 2 of the 3 readings at screening or with a mean QST Heat sensation temperature assessment of 48.5°C or less based on the average of the last 2 of the 3 readings on the treated cheek at Baseline during Session 1;

- f. Subjects must agree to refrain from ingesting any systemic or topical analgesic medication for 3 days or 5 half-lives of the drug prior to and during each study session and alcohol for 1 day prior to and during each study session;
- g. Subjects must agree to refrain from using mouth rinses, cough drops or throat lozenges on the day of each test session;
- h. Female subjects must be physically incapable of childbearing potential (postmenopausal for more than 1 year or surgically sterile) or practicing an acceptable method of contraception (hormonal, barrier with spermicide, intrauterine device, vasectomized or same sex partner, or abstinence). Subjects using hormonal birth control must have been on a stable dose of treatment for at least 30 days and received at least 1 cycle of treatment prior to randomization. At Screening and at Baseline of both sessions, all females of childbearing potential must have a negative urine pregnancy test and not be breastfeeding;
- i. Negative urine drug screen for drugs of abuse at Screening and at Baseline for each Study Session. A positive drug screen result may be permitted if the subject has been on a stable dose of an allowed medication for >30 days;
- j. The subject is capable of reading, comprehending, and signing the informed consent form.

**EXCLUSION
CRITERIA:**

- a. Subjects with a history of any significant hepatic, renal, endocrine, cardiac, neurological, psychiatric, gastrointestinal, pulmonary, hematologic, or metabolic disorders, including glaucoma, diabetes, emphysema, and chronic bronchitis;
- b. Subjects with a history of any type of cancer other than skin related cancers;
- c. Subjects with conditions that affect the absorption, metabolism, or passage of drugs out of the body, (e.g., sprue, celiac disease, Crohn's disease, colitis, or liver, kidney, or thyroid conditions);
- d. Subjects with any history of alcohol or substance abuse (including a positive drug screen test);
- e. Subjects that currently have or have a history of uncontrolled hypertension;

- f. Subjects with a known hypersensitivity to any local anesthetic drug;
- g. Subjects with a hematocrit level significantly below the normal range on the screening laboratory examination (as judged by the PI) or a pulse oximetry reading of less than 96% at screening or at Baseline of either session;
- h. Subjects with any clinically significant abnormal lab result (as judged by the PI);
- i. Subjects with any condition or history felt by the Investigator to place the subject at increased risk;
- j. Subjects who have smoked or chewed tobacco-containing substances within 6 months prior to the start of the study;
- k. Subjects judged by the Investigator to be unable or unwilling to comply with the requirements of the protocol;
- l. Subjects who have used an investigational drug within 30 days prior to entering the study;
- m. Subjects who have donated blood within 3 months prior to the start of the study;
- n. Subjects who have previously participated in the trial;
- o. Subjects who are members of the study site staff directly involved with the study or a relative of the Sponsor or other personnel involved with the study.

ECG TIMES: ECGs will be taken at screening, and during treatment visits at Baseline (Time 0, within 1 hour prior to drug administration) and then immediately after the 1 hour test session.

SAFETY EVALUATION: All potential subjects will receive a blood chemistry test and urine drug screen at the screening visit. As a safety precaution, at each study session, blood samples will be taken at Baseline and 1 hour after study medication to measure methemoglobin levels.

Pulse oximetry will be performed at screening, and at each session at Baseline, and 10, 20, 30, 40, 50 and 60 minutes after drug administration.

All the medications being evaluated in this study are marketed local anesthetic products in the United States and are being used within their currently indicated dosages and indications. Adverse experiences will be recorded as they occur during the treatment phase of the study and if voluntarily reported by the subject within 3 days following completion of the first study session and within 15 days following the end of the subject's participation in the study. Treatment-emergent AEs will be summarized by incidence. The events will be coded using the Medical

Dictionary for Regulatory Activities (MedDRA) and summarized by system organ class (SOC) and preferred term (PT).

Irritation and/or infection at the site of application will be assessed. The severity, relationship to treatment, action taken, and outcome of the events will be documented. The incidence of all adverse events and drug-related adverse events will be evaluated. In the event of any health related emergency, the clinical site will have a trained medical staff with a fully equipped emergency crash cart.

STATISTICAL ANALYSIS:

Primary Efficacy Endpoints:

- Duration of anesthesia as measured by PPT for one spray CTY-5339-A compared to the one spray CTY-5339-CB
- Duration of anesthesia as measured by QST Heat for one spray CTY-5339-A compared to the one spray CTY-5339-CB

Secondary Efficacy Endpoints:

- Duration of anesthesia as measured by PPT and QST Heat for the two spray CTY-5339-A compared to the one spray CTY-5339-CB plus one spray CTY-5339-P
- Duration of anesthesia as measured by PPT and QST Heat for the two spray CTY-5339-A compared to the one spray CTY-5339-A
- Onset of anesthesia for PPT and QST Heat
- Percentage of responders for PPT and QST Heat for both onset and duration
- Percentage of responders for PPT and QST Heat at each time point

Safety Data:

- SBP, DBP, and HR at Baseline and at the end of each 60-minute test session,
- Pulse oximetry at Baseline and at 10, 20, 30, 40, 50 and 60 minutes after drug administration,
- 12 Lead ECG at Baseline and at the end of each 60-minute test session,
- Methemoglobinemia at Baseline and at the end of each 60-minute test session, and
- Analysis of incidence and severity of all adverse events

For the PPT, a “Responder” is defined based on an assessment of “No Pain” or “Less Pain” in response to the pain stimulus at each observation time when compared to the non-treated site, (See Appendix 2). The % of responders at each time point will be compared between treatments. In addition, the % of subjects who have Onset (and Duration) will also be compared between treatments.

For the QST, a “Responder” is defined as follows: If the average heat

temperature at each time point is greater than the average heat temperature at Baseline, then the subject at that time point will be considered a “Responder”. The % of responders at each time point will be compared between treatments. In addition, the % of subjects who have Onset (and Duration) will also be compared between treatments.

Data will be generated as the difference in response between the control, non-treated site and the active treatment site within in each subject.

ANOVA and pairwise t-tests will be used to compare CTY-5339-A treatment groups to the CTY-5339-CB treatment group.

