APPENDIX 1: DESCRIPTION OF TESTING METHODS

Appendix 1A: Pin Prick Test (PPT)

Oral Mucosa sensation directly over the circumscribed sites will be assessed with a 90-mm, 26-gauge pencil-point spinal needle (Polymedical; Temena S.A., Bondy, France or its equivalent) at Screening, Baseline and predetermined intervals after application of drug. To standardize the methodology, all tests are performed by holding the needle at its hub and orienting it perpendicular to the oral mucosa surface. Pressure is applied until the needle shaft bows slightly. At screening a numerical score on a 0 – 10 pain intensity scale (NRS) is recorded for each cheek. After study drug administration, subjects are instructed to rate the pinprick sensation perceived over the circumscribed treatment site compared to that perceived at the contra-lateral circumscribed, non-treated site and to report the sensation as none, less, or similar/more to the non-treated site. Reports of none or less indicate analgesia, while a report of similar/more indicates complete regression of analgesia. At each observation, 3 pin pricks are performed first on the non-treated side, and then on the treated side. For each cheek, the first pin prick will not be used for analysis. Of the remaining two pin pricks, the one with the most severe pain rating will be used for the data analysis.

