APPENDIX 2: CRITERIA FOR A “RESPONDER”

PPT:

Based on “No Pain” or “Less Pain” response to the pain stimulus at each observation time when compared to the non-treated site, subjects will be classified as “Responders” or “Non Responders”. At each observation, 3 pin pricks will be performed at each site (first on the non-treated cheek and then on the treated cheek). The first pin prick will not be used for analysis. Of the remaining two pin pricks, the one with the most severe pain rating will be used for the data analysis. If the most severe pain rating at that time point is “No Pain” or “Less Pain”, then the subject at that time point is a “Responder”.

QST:

The actual temperature data will be recorded at each time point. Temperatures will be recorded for "first sensation of tingling, warmth, heat, or pain". Scores will be censored at 51°C, if no response is obtained. If the average heat sensation temperature at each time point is greater than the average heat sensation temperature at Baseline, then the subject at that time period will be considered a “Responder”.

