9.2 Inclusion Criteria

Individuals may be included in the study provided they meet all of the following inclusion criteria:

- a. Male and female subjects between 18-75 years of age with a Body Mass Index (BMI) ≤ 32 ;
- b. Subjects are ASA Category I or II and are in normal physical health as judged by physical and laboratory examinations;

- c. Subjects with normal appearance of the oral mucosal tissues;
- d. At screening and at Baseline during Session 1, subjects with PPT scores on both cheeks of at least “3” (on a 10 point NRS) on the last 2 of 3 readings, 1 of which must be a score of at least “4”;
- e. Subjects with mean QST Heat sensation temperature assessments on both cheeks of 48.5°C or less based on the average of the last 2 of the 3 readings at screening or with a mean QST Heat sensation temperature assessment of 48.5°C or less based on the average of the last 2 of the 3 readings on the treated cheek at Baseline during Session 1;
- f. Subjects must agree to refrain from ingesting any systemic or topical analgesic medication for 3 days or 5 half-lives of the drug prior to and during each study session and alcohol for 1 day prior to and during each study session;
- g. Subjects must agree to refrain from using mouth rinses, cough drops or throat lozenges on the day of each test session;
- h. Female subjects must be physically incapable of childbearing potential (postmenopausal for more than 1 year or surgically sterile) or practicing an acceptable method of contraception (hormonal, barrier with spermicide, intrauterine device, vasectomized or same sex partner, or abstinence). Subjects using hormonal birth control must have been on a stable dose of treatment for at least 30 days and received at least 1 cycle of treatment prior to randomization. At Screening and at Baseline of both sessions, all females of childbearing potential must have a negative urine pregnancy test and not be breastfeeding;
- i. Negative urine drug screen for drugs of abuse at Screening and at Baseline for each treatment session. A positive drug screen result may be permitted if the subject has been on a stable dose of an allowed medication for >30 days;
- j. The subject is capable reading, comprehending, and signing the informed consent form.

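### Pin-prick response is judged only against the untreated cheek, and neither Baseline eligibility nor the analysis accounts for a cheek difference present before dosing

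*Combined protocol and SAP*

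**What the plan says.** **Rating after dosing.** The Synopsis states that "on the treated cheek, the three repetitions will be compared to the non-treated cheek as" one of three categories: no pain, less pain, or similar/more. Appendix 1A gives the same instruction: "subjects are instructed to rate the pinprick sensation perceived over the circumscribed treatment site compared to that perceived at the contra-lateral circumscribed, non-treated site". Either of the first two categories makes a Responder (Appendix 2: "when compared to the non-treated site, subjects will be classified as" Responders or Non Responders). The treated cheek gets no 0-10 score after dosing.

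**Baseline.** The Synopsis says "At Baseline, pin pricks on both cheeks will be assessed using a 0 (no pain) to 10 (severe pain) NRS". For each cheek, "both of the last 2 Baseline assessment pin pricks must have a minimum score of" 3, and one must reach 4. Section 9.2 ("subjects with PPT scores on both cheeks of at least" 3), section 11.2.2 and section 11.7 use the same minimum. None of them limits the difference between cheeks.

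**Scoring.** The first of three pricks is dropped. "Of the remaining 2 pin pricks, the one with the most severe pain rating will be used for analysis".

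**Side.** "Each session will use a different side of the cheek" (Synopsis; also section 9). Left or right is set by the randomization code (Synopsis, sections 9 and 10.2).

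**Analysis.** Section 13.3 only tabulates Baseline efficacy scores by treatment group. Section 13.5 names ANOVA, chi-square and log-rank comparisons with treatment effects only. The last lines of the Synopsis mention the difference between control and treated sites within a subject, but not its change from Baseline.

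**The concern.** The PPT endpoint assumes that the two cheeks feel alike before the drug is given, and nothing in the plan checks or corrects for this. A subject who scores 8 on the control cheek and 4 on the cheek to be treated passes Baseline. That subject could truthfully report less pain at every time point with no drug effect, which would be recorded as an early onset and a duration running to 60 minutes. For heat, the Synopsis and Appendix 2 avoid the problem by requiring a rise over Baseline. PPT has no equivalent.

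The crossover does not remove the effect. The side changes between sessions, so a stable left-right difference acts in opposite directions at a subject's two sessions and adds to the spread of the CTY-5339-A minus CTY-5339-CB difference. Full-length durations that are not due to drug, in both arms, also shrink the observed difference. Section 13.1 gives no effect size, SD or power, so the plan shows no margin to absorb this.

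**Working it through.** **Step 1. What the Baseline rule permits (documents only).** Two scores from 3 to 10 on one cheek give 8 x 8 = 64 ordered pairs. Dropping (3, 3) leaves 63. The number of pairs whose worse score is m is 2m - 5, that is 3, 5, 7, 9, 11, 13, 15 for m = 4 to 10, which sums to 63. Two cheeks give 63 x 63 = 3,969 patterns.
- Equal worse scores: 9 + 25 + 49 + 81 + 121 + 169 + 225 = 679.
- Treated cheek's worse score already lower: (3,969 - 679) / 2 = 1,645, or 41%.
- Lower by at least 2 points: 1,095, or 28%. The largest gap is 10 - 4 = 6.

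These are shares of permitted patterns, not expected frequencies in subjects.

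**Step 2. Size under assumed asymmetry.** From the documents: the PPT time grid, onset by 10 minutes, failure at two consecutive time points from 10 minutes on, the 60-minute limit, the more severe of two pricks, randomized side, and side switched between sessions. Assumed, because the documents give no figures: a stable left-right difference with mean 0 and SD s; reading noise SD 0.5 points; *less* means at least 1 point lower; a drug effect of 4 points; true mean durations of 35 min (CTY-5339-A) and 25 min (CTY-5339-CB), each with SD 6 min.

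Because the more severe prick counts, both readings must be at least 1 point lower. The chance of being *less* before dosing is the average of Φ((-1 - a)/0.5)² over a ~ N(0, s²). At s = 0 this is Φ(-2)² = 0.0228² = 0.0005, which is effectively zero.

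| Left-right SD s (points) | 0 | 0.5 | 1.0 | 1.5 |
|---|---|---|---|---|
| Sessions already *less* before dosing | 0% | 2% | 12% | 20% |
| Observed mean difference (true 10 min) | 10.1 | 10.0 | 9.2 | 7.7 |
| SD of within-subject difference (min) | 8.8 | 9.5 | 15.6 | 22.9 |
| SD after adjustment for Baseline cheek difference (min) | 8.8 | 9.4 | 11.7 | 12.2 |
| SE with 38 pairs, unadjusted (SD/√38) | 1.4 | 1.5 | 2.5 | 3.7 |
| SE with 38 pairs, adjusted | 1.4 | 1.5 | 1.9 | 2.0 |

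The 38 pairs are the one-spray CTY-5339-A exposures stated in the Synopsis. Adjustment means regressing the paired duration difference on the between-session difference in the Baseline cheek gap.

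**Step 3. Does it favour a product?** A separate simulation used 38 subjects, the same scoring rules and equal drugs (median 15 min each). A paired t-test rejected in 4% to 6% of runs for every s from 0 to 2 points, so there is no built-in advantage. With medians of 22 and 15 min, log-rank power was 95%, 91%, 48% and 30% for s = 0, 0.5, 1.0 and 1.5.

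**The case against.** **Most of the case on the other side concerns size, and much of it stands.**
- A reader might infer that the design favours CTY-5339-A. It does not: side is randomized, and Step 3 shows a paired test keeping its level.
- A reader might infer that the noise is certainly large. The documents do not show this. At an asymmetry SD of 0.5 points the SD rises only from 8.8 to 9.5 min, with no visible dilution. The reversal between sessions also requires the asymmetry to last over the 4 to 14 days between them.
- A reader who models one reading per time point would get 2%, 8%, 19% and 26% of sessions already *less*. That overstates the problem, because the protocol scores the more severe of two pricks.
- A reader might take the 41% in Step 1 as a rate of false Responders. It is only a count of patterns that the rule allows.
- A control cheek tested at the same time point has a real benefit: it absorbs drift in pain rating within the session, which comparison with Baseline alone would not. This is a reason to keep the comparison and adjust it.
- The study is proof of concept, section 13.1 accepts a clear trend, and section 13.6 lets either co-primary endpoint carry success. This lowers the stakes, although extra noise and dilution can also hide a trend.

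None of these points supplies a limit on the Baseline cheek difference or an analysis that uses it. The control-versus-treated difference at the end of the Synopsis is not a Baseline adjustment. It also cannot be turned into one by subtraction, because the treated cheek has no numerical score after dosing.

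**Conclusion.** The point holds as one of precision and misclassification, not of bias. The text alone establishes that a subject can enter as a Responder by the endpoint's own definition, that switching sides makes a stable asymmetry act on one session and not the other, and that no planned analysis uses the Baseline difference. How much this matters depends on an asymmetry that the documents do not give. Under the assumptions in Step 2 it is negligible at a left-right SD of 0.5 points or below. At 1.0 point the SD of the paired difference is about 1.8 times its symmetric value (15.6/8.8), and at 1.5 points about 2.6 times (22.9/8.8). Adjustment recovers most of that loss: 11.7 and 12.2 min in those two cases.

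**What to change.** **Primary change, section 13.5.** Add each session's Baseline treated-minus-control NRS difference as a covariate in the PPT duration analysis, using the more severe of the last two pricks on each cheek. Name the model and let it use the within-subject pairing, for example a mixed-model ANCOVA of duration or a Cox model stratified by subject. The stated log rank takes no covariate, so wording alone within that test will not do.

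**Sensitivity analysis.** Report PPT duration without sessions in which the treated cheek already scored lower at Baseline, with the number excluded per product. With switched sides this will often drop one session of a pair, so it should support the primary analysis and not replace it.

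**Not recommended as a continuation rule.** Requiring a rating of similar/more at each session's Baseline would make about 23% to 40% of subjects fail one Baseline (s = 1.0 to 1.5). About half of them would fail at Session 2, after a dose, so their pairs would be lost. The three-category question may be recorded at Baseline for the sensitivity analysis only.

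**Cost.** A little more analysis work and a model beyond the stated log rank, to be fixed before unblinding. The covariate needs no new data, because section 11.2.2 already puts the Baseline scores on the CRF. Recording the optional question adds one item and no extra pricks.
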